3. STUDY SETTING AND POPULATION

3.1 Study setting

The enrollment period will be between 1 September 2017 and 30 June 2020. The patients recruited were treated in an outpatient setting in the multidisciplinary chronic pain center in Lanaken, Campus St. Barbara, ZOL. Patients with chronic knee pain who qualify for a conventional radiofrequency treatment of the genicular nerves were recruited. Prior a diagnostic block was performed and in case of positive results patients were treated with conventional radiofrequency ablation. Follow up in the pain clinic consisted of a minimum of one consultation after treatment at six weeks post procedure. Further follow up was planned according to the needs of the patient at the pain clinic, orthopedist or general practitioner.

3.2 Population

3.2.1 Inclusion criteria

1. All patients with chronic knee pain who qualify for a conventional RF treatment of the genicular nerves

3.2.2 Exclusion Criteria

Patients will be excluded from participating in the study if they meet any of the following exclusion criteria:

1. Refusal to participate
2. A negative diagnostic block with lidocaine 2% 1 ml of the three genicular nerves defined as less than 50% pain reduction
3. Chronic widespread pain

4. STUDY OBJECTIVES

4.1 **The primary objective** of this study is to evaluate the treatment success of the conventional radiofrequency treatment of the genicular nerves in patients on patients diagnosed with chronic knee pain due to osteoarthritis of the knee or PPSP at six weeks post treatment. Treatment success is defined as a global perceived effect of at least 50% at measurement time point compared to baseline.

4.2 **The secondary objectives** are:

- Evaluation of treatment effect at a third time point at the end of the inclusion period
- Subgroup analysis of treatment success based on indication to treatment
- Evaluation of subjective functional improvement
- Evaluation of change in analgesics
- Estimation of the duration of effect of the treatment
- Adverse event

5. STUDY ENDPOINTS

5.1 Primary endpoint:

Proportion of patient with treatment success at week 6 defined as a global perceived effect of $\geq 50\%$ compared to baseline.

5.2 Secondary endpoints:

- Proportion of patients with treatment success at third time point defined as a global perceived effect of $\geq 50\%$ compared to baseline.
- NRS reduction at week 6 and at the third time point.
- Subjective physical functioning at week 6 and at the third time point.
- Duration effect of the treatment defined as the period with a GPE of $\geq 50\%$.
- Change in use of strong opioids at week 6 and at the third time point.
- Safety: number/type of adverse events.

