2. STUDY DESIGN

2.1 Study design

This study is designed as a retrospective longitudinal cohort study of patients treated with a radiofrequency treatment of the genicular nerves in a single-center (ZOL, Genk) between 1 September 2017 and 30 June 2020. Each knee will be considered as a unique observation, and bilateral procedures were assessed specific to each knee treated. Data retrieved from the patient files will be collected at baseline, 6 weeks post-intervention and telephonically at a third time point which ranges from 6 weeks to 3 years after the procedure. The following demographic and clinical data will be collected at baseline: patient age, sex, NRS score, length of symptom duration, indication for the procedure, use of strong opioids, history of previous knee surgery and the referring physician. Strong opioid analgesics are defined as all opioids excluding tramadol and codeine.

Data collected at 6 weeks post-intervention will include: NRS, GPE, adverse events, and concomitant use of strong opioids.

Patient's data will be collected at a third time point. Written informed consent will be obtained by mail prior to contact by phone. After receiving informed consent, patients will be contacted by telephone and data will be gathered on the same variables as at 6 weeks post-intervention and on subjective functional outcome.

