2.2 Questionnaire

At the third time point patients will be contacted by phone, after receiving written informed consent by mail. The study and its rationality will be introduced together with the main objectives. The input needed from the patients will be communicated and an oral informed consent will be requested. In case of a positive input the following questions will be asked:

- How much pain do you experience at the moment in the knee where the procedure was performed in a scale of zero to ten where zero is 'no pain' and ten is 'unbearable pain'?
- Is the pain in the knee tolerable or not?
- How much effect do you still perceive at the moment expressed in percent between 0 and 100%?
- How long do you think the treatment worked or is there still effect?
- Do you experience at the moment functional improvement in comparison with before the treatment?
- Which pain medication are you using at the moment?
- Did you experience any adverse events?

The conversation will be executed in the Dutch language.

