7. STATISTICAL CONSIDERATIONS

Data will be presented as mean values and standard deviations or as median values and interquartile range (IQR) depending on the distribution of the data. The average post-treatment pain score will be estimated using linear mixed effects regression analysis using time since treatment as independent variable. We will use this multilevel approach as (most) patients contribute more than one post-treatment pain score to the dataset. This way, we will be able to estimate the 3 and 6 months effect of RF treatment. The statistical analysis will be performed using SPSS.

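### Third-contact GPE success is one proportion pooled over 6 weeks to 3 years of follow-up, so it describes no particular time and, if success changes with time, depends on the accrual pattern as well as on RF

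*Combined protocol and SAP*

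**What the plan says.** - **Endpoint.** Section 5.2 defines the "Proportion of patients with treatment success at third time point defined as a global perceived effect of" at least 50% compared with baseline. The synopsis has the same endpoint. Neither attaches a time to it.
- **Timing.** Section 2.1 collects these data "telephonically at a third time point which ranges from 6 weeks to 3 years after the procedure". Section 4.2 ties the contact to the calendar: "Evaluation of treatment effect at a third time point at the end of the inclusion period". Each knee's follow-up is therefore set by its treatment date, within the 1 September 2017 to 30 June 2020 window.
- **What is asked.** Section 2.2 asks "How much effect do you still perceive at the moment expressed in percent between 0 and 100" percent. This is the patient's status on the day of the call.
- **Analysis.** Section 7 says: "The average post-treatment pain score will be estimated using linear mixed effects regression analysis using time since treatment as independent variable". It then adds: "This way, we will be able to estimate the 3 and 6 months effect of RF treatment". These are the only horizons named, and they come from the pain-score model. Section 7 gives no method for the GPE proportion.
- **Duration.** Section 5.2 also lists the period with GPE of at least 50%. The questionnaire obtains it by asking "How long do you think the treatment worked or is there still effect".
- **Unit.** Section 2.1 states: "Each knee will be considered as a unique observation, and bilateral procedures were assessed specific to each knee treated".

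**The concern.** A proportion based on current status means something only with a time attached. Here a knee called at 6 weeks, which is already the primary time point, and a knee called at almost 3 years enter the same numerator and denominator with equal weight. A reader of the result cannot tell whether it describes success at half a year, one year or two years.

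If success changes with time since treatment, the pooled value is an average over whatever follow-up times the accrual produced. Two centres with an identical treatment effect but different referral growth would then report different long-term success. The plan itself treats time as relevant: it models it for pain, and it makes duration of effect an endpoint. At stake is how the study's only longer-term success proportion is interpreted and compared with other reports.

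**Working it through.** The documents give no rate, sample size or expected value for this endpoint, so there is no planned figure to reproduce. The check has two parts: the follow-up range, from stated dates, and the sensitivity to accrual, from assumed inputs.

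**Follow-up range (stated dates).** 1 September 2017 to 30 June 2020 is 1,033 days. One calling round 6 weeks (42 days) after the last treatment gives follow-up from 42 days to 1,033 + 42 = 1,075 days. That is 1.38 to 35.32 months at 30.4375 days per month, or 2.94 years at most. The stated 3-year limit leaves 3 × 365.25 − 1,075 = 20.75 days of slack. The range in section 2.1 is therefore what one calling round soon after accrual closes would produce.

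**Assumptions.** Success is 60% at week 6 and then halves every *h* months: S(t) = 0.6 × 0.5^((t − 1.38)/h). Three accrual shapes over the 33.94-month window are compared:
- uniform: median follow-up 18.3 months;
- late-skewed (accrual rising linearly): median 11.3 months;
- early-skewed (accrual falling linearly): median 25.4 months.

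**Formula.** With x = ln 2 × 33.94/h, the mean of S(t)/0.6 is
- uniform: m = (1 − e^(−x))/x
- late-skewed: L = (2/x)(1 − m)
- early-skewed: E = 2m − L

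For h = 12: x = 1.960, m = 0.438, L = 0.573, E = 0.303. Multiplied by 0.6 these give 0.263, 0.344 and 0.182.

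| Assumed course | Uniform | Late-skewed | Early-skewed | Range (points) |
|---|---|---|---|---|
| Halving every 6 months | 15.0% | 23.0% | 7.0% | 16.0 |
| Halving every 12 months | 26.3% | 34.4% | 18.2% | 16.2 |
| Halving every 24 months | 38.2% | 44.4% | 32.1% | 12.3 |
| No decline | 60% | 60% | 60% | 0 |

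Starting from 40% at week 6 with 12-month halving, the figures are 17.5%, 22.9% and 12.1%, a range of 10.8 points. The call date matters little inside the plan: calls 21 days later move the uniform 12-month-halving figure from 26.3% to 25.3%.

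**By contrast, a fixed time does not depend on accrual.** Under 12-month halving the same model gives 45.9% at 6 months, 32.5% at 12 months and 16.2% at 24 months, whatever the accrual shape.

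**Limits of time bands.** Under 12-month halving, success falls from 60% to 32% inside a band running from 6 weeks to 12 months, so that band is still a mixture. Bands also hold different patients. Suppose there is no decline at all, but success rises linearly from 50% in the first to 70% in the last patients treated. With uniform accrual, bands of up to 12, 12 to 24 and over 24 months would then show 67%, 60% and 53%, a false decline.

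**The case against.** The strongest case on the other side has five parts.

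- **The range is disclosed, and the figure is a valid description.** This is one single-arm cohort with one realised accrual pattern, and no test or decision rests on the endpoint. That stands, and it is why the severity is low. A reader might infer that the 16-point range is an error in this study's estimate. It is not: it compares hypothetical cohorts under assumed rates. Disclosing the range still does not tell a reader which time the proportion describes.
- **Accrual dependence is conditional.** A reader might infer that the figure must depend on accrual. The documents give no rate of decline, and with a constant success rate pooling is harmless. Only the missing horizon follows from the text alone.
- **The duration endpoint addresses persistence.** It does so in part. A reader might infer that duration has no planned analysis, but the general rule in section 7 (mean and SD, or median and IQR) nominally covers it. That rule does not handle knees that still have an effect at the call, whose duration is incomplete. The data also rest on recall. In any case, a duration summary does not give the success proportion a time.
- **Section 7 is brief on every GPE proportion, including the primary.** True, but the primary has its time fixed at week 6 and the third-contact proportion does not.
- **Splitting by time costs precision and mixes durability with treatment period.** This stands. If 60 knees are assumed, a band with 35% of them holds 21, and 5 of 21 successes has a 95% Wilson interval of about 11% to 45%. It argues for a model on continuous time rather than bands as the main presentation, and for cautious wording.

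**Conclusion.** The point holds as a low-severity one. Sections 5.2, 2.1, 4.2 and 7 together yield a long-term success figure with no defined horizon. If success changes with time since treatment, the figure also reflects the accrual pattern. Its possible size is about 12 to 16 points between plausible accrual shapes if success is 60% at week 6 and halves every 6 to 24 months, and zero if it does not change. The week-6 rate, the halving times and the accrual shapes are all assumptions. The real accrual pattern, which the documents do not show, decides where this study falls.

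A reader might infer that the study's main conclusion is at risk. The documents do not support that: the primary endpoint is fixed at week 6, and the pain score already has a model on time since treatment.

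**What to change.** In sections 5.2 and 7:

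1. Report the distribution of time from treatment to the third contact (median, IQR, range).
2. Present third-contact GPE success against time since treatment, preferably from a logistic model on that variable that allows for two knees in one patient. Give estimates with confidence intervals at a few times chosen before the analysis.
3. Add broad time bands only as a descriptive supplement, where numbers allow.
4. Describe the result as cross-sectional. Each knee gives one third-contact value, and different follow-up times hold patients treated in different periods, so this is not a within-patient decline curve.
5. Because contact depends on consent returned by mail (section 8), give the number contacted and the number responding by follow-up time.

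The cost is a few lines of text. Time since treatment is already needed for the pain-score model, so the success analysis needs no new outcome data; the response counts need only a contact log. The downsides are lower precision at each time, cohort and response differences mixed with durability, and a possibly less favourable long-term figure.

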Main study endpoints: The main study outcome is the proportion of patients with a global perceived effect of at least 50% at 6 weeks post intervention. Secondary outcomes include reduction in pain intensity, measured by Numeric Rating Scale (NRS) at six weeks and at a third time point, global perceived effect at a third time point, subjective change in physical functioning, duration effect of the treatment, use of strong opioids, and adverse events.

PROTOCOL SYNOPSIS

Study Title	A retrospective single-center cohort study on patients with chronic knee pain treated with conventional radiofrequency of the genicular nerves.
Funder	ZOL Genk
Study Objectives	
Primary objective
 
• To evaluate treatment success of the conventional radiofrequency ablation at week 6 
Secondary objective
 
• Evaluation of treatment effect at a third time point at the end of the inclusion period• Subgroup analysis of treatment success based on indication to treatment• Evaluation of subjective functional improvement• Evaluation of change in analgesics• Estimation of the duration of effect of the treatment• Adverse events
Study Design	Retrospective single-center cohort study
Subject Population Key criteria for Inclusion and Exclusion:	
Inclusion Criteria
 
1. All patients with chronic knee pain who qualify for a conventional RF treatment of the genicular nerves 
Exclusion Criteria
 
1. Refusal to participate2. A negative diagnostic block with lidocaine 2% 1 ml of the three genicular nerves defined as less than 50% pain reduction3. Chronic widespread pain
Time	Patients treated with conventional RF treatment between 1 September 2017 and 30 June 2020.
Study endpoints	
1. Primary endpoint:
- Proportion of patients with treatment success at 6 weeks defined as GPE of $\geq 50\%$ compared to baseline.2. Secondary endpoints:
- Proportion of patients with treatment success at third time point defined as GPE of $\geq 50\%$ compared to baseline.- NRS reduction at week 6 and at the third time point- Subjective physical functioning at week 6 and at the third time point- Duration effect of the treatment defined as period with a GPE of $\geq 50\%$- Change in strong opioid use at week 6 and at the third time point- Safety: number/type of adverse events

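### Duration of effect is defined by a 50% threshold that the telephone question does not ask about, and Section 7 has no rule for effects still ongoing at the call

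*Combined protocol and SAP*

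**What the plan says.** - **Definition.** Section 5.2 lists "Duration effect of the treatment defined as the period with a GPE of" 50% or more, and the protocol synopsis has the same definition ("Duration effect of the treatment defined as period with a GPE of" 50% or more). Section 4.2 makes estimating the duration of effect a secondary objective.
- **Measurement.** The only duration item in Section 2.2 is "How long do you think the treatment worked or is there still effect". The only percentage item concerns the present: "How much effect do you still perceive at the moment expressed in percent between 0 and 100" per cent. Sections 2.1 and 6 place GPE at week 6 and at the call, and nowhere else. The schedule in Section 6 has no row for duration.
- **Follow-up.** Data are collected "telephonically at a third time point which ranges from 6 weeks to 3 years after the procedure". Section 3.1 states "The enrollment period will be between 1 September 2017 and 30 June 2020", and Section 4.2 sets the third time point at the end of that period.
- **Unit.** Section 2.1 states "Each knee will be considered as a unique observation", so one patient can contribute two durations.
- **Analysis.** Section 7 describes data by mean and SD or by median and IQR, and fits a linear mixed model to pain scores. It names no method for duration.

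**The concern.** There are two separate gaps.

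**Threshold.** The endpoint needs the time at which GPE dropped below 50%. The patient is asked only how long the treatment worked. A patient who counts any remaining benefit will report a longer time than the definition; one who counts only strong relief will report a shorter one. The documents do not fix the reading, so the direction of the difference is unknown.

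**Ongoing effects.** The question itself allows that the effect persists. Such a knee gives only a lower bound on duration, and that bound depends on how long ago the patient was treated. Section 7 would let an analyst count the bound as a completed duration, leave the knee out, or rank it longest. Counting as completed shortens the mean and usually the median, and so does leaving out. Ranking longest can lengthen the median.

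At stake is the figure that answers a named secondary objective.

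**Working it through.** The documents state no duration, response rate or sample size, so there is no planned figure to reproduce. The textual gap needs no arithmetic. Its possible size is illustrated below.

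**1. What the planned data identify.**
- GPE below 50% at week 6: any end of the defined period lies before week 6.
- At least 50% at week 6 and below 50% at the call: the end lies somewhere between the two.
- At least 50% at the call: the end lies after the call.

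For no knee is the end date itself observed.

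**2. Threshold mismatch.** Assume GPE falls linearly from g0 to 0 and the patient reads the question as GPE at least r. Recalled time divided by defined time is (g0 − r)/(g0 − 50). With g0 = 80:
- any effect (r = 0): 80/30 = 2.7
- r = 30: 50/30 = 1.7
- r = 70: 10/30 = 0.33

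If the effect is lost abruptly the ratio is 1.

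**3. Call lag.** From 1 September 2017 to 30 June 2020 is 1,033 days, or 1,033/30.44 = 33.9 months. One calling round 6 weeks (1.38 months) after the end gives lags of 1.4 to 35.3 months, which agrees with the range in Section 2.1. Treatments are assumed evenly spread, so the lag C is uniform on that range.

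**4. Handling of ongoing effects.** Assume a share p of knees falls below 50% by week 6 (uniform over 0–42 days) and the rest last 6 weeks plus an exponential time with median m months. Beyond week 6:
- S(t) = (1 − p) × 2^(−(t − 1.38)/m)
- G(t) = P(C > t) = (35.3 − t)/33.9

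For p = 20%, m = 12:
- True median: S(t) = 0.5 gives t = 1.38 + 12 × log2(0.8/0.5) = 1.38 + 8.14 = 9.5.
- Counted as completed: S(t) × G(t) = 0.5 gives t = 6.6. Check: S = 0.591, G = 0.846, product 0.50.
- Dropped: the median among knees whose effect has ended is 4.5.
- Ranked longest: the time by which half of all knees have an observed end is 11.2.

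Medians in months:

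| p | m | Ongoing at call | True | Completed | Dropped | Ranked longest |
|---|---|---|---|---|---|---|
| 20% | 6 | 20% | 5.4 | 4.6 | 4.0 | 5.8 |
| 20% | 12 | 35% | 9.5 | 6.6 | 4.5 | 11.2 |
| 20% | 18 | 45% | 13.6 | 8.0 | 4.1 | 18.6 |
| 40% | 12 | 26% | 4.5 | 3.45 | 1.3 | 4.7 |
| 60% | 12 | 17.5% | 1.15 | 1.15 | 0.95 | 1.15 |

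In the last row only dropping moves the median, but the mean is 7.9 true against 4.9 completed and 3.1 dropped. A 36-month window changes the p = 20%, m = 12 row by at most 0.1.

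**5. Does Kaplan-Meier help?** Simulation: 3,000 studies of 100 patients, 20% bilateral, within-patient correlation 0.6 (all assumed). With exact 50%-anchored durations, the root mean squared error (RMSE) of the median at p = 20%, m = 12 is 1.9 months for Kaplan-Meier, 3.0 for completed, 5.1 for dropped and 3.9 for ranked longest. At p = 40%, Kaplan-Meier has 1.7 against 1.5 for completed: centred correctly, but no more accurate.

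**The case against.** The text is not in dispute. The case against is about weight and remedy.

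- **Limited consequence.** This is one of six secondary endpoints in a descriptive single-arm cohort, with no test planned on it, and the question is openly one of recall. This stands, and it keeps the point below anything touching the primary endpoint. It does not make the recalled time the defined endpoint.
- **Assumed magnitudes.** They range from large to nil. This stands: confidence attaches to the gap, not to any one bias.
- **The remedy does not always win.** Kaplan-Meier is no more accurate than the completed-times median at p = 40%. An interval-censored estimate from the two GPE records has RMSE 3.5 against 3.0 for completed times at p = 20%. Both stand. However, that 3.0 assumes exact 50%-anchored durations, which the current question does not supply.
- **Patient-level resampling.** Coverage of the 95% interval was 93% resampling patients against 91% resampling knees, from 500 studies. Each figure has a Monte Carlo standard error of 1.1 to 1.3 points, so the demonstrated gain is small. The reason to do it is that two knees from one patient are not independent.
- **Scoring of early failures.** The illustration spreads early failures over the first six weeks. If all were scored 0, the dropped median at p = 40% would be 0, and at p = 60% the true, completed and dropped medians would all be 0. The p = 20% results barely change. Knees below 50% by week 6 need not all have failed ever to reach 50%.
- **Unstated conditions.** Kaplan-Meier needs call lag to be unrelated to duration, which drift in selection or technique over 34 months could break. Repeat treatment, knee surgery before the call, and contradictory answers also need rules. This stands and is taken up in the fix.

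**Conclusion.** The concern holds. Followed as written, the plan reports a recalled duration without a threshold in place of the period with GPE at least 50%, and leaves open a choice that can move the result materially. Under the illustrative assumptions (p = 20%, m = 12, even spread of treatments, one calling round), the reported median could be anywhere from 4.5 to 11.2 months against a true 9.5. With many early failures the median is hardly affected, though the mean still is. The threshold mismatch could act in either direction, from 0.33 to 2.7 times under linear decline from 80%, or not at all if effect is lost abruptly. The actual bias cannot be known from the documents. This should be corrected.

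**What to change.** **If calls have not been made.** Reword the duration item in Section 2.2 to ask, for each knee, how long the effect was at least 50% and whether it still is. In Section 7, estimate the duration by Kaplan-Meier, right-censored at the call when GPE is still at least 50%, with duration 0 if 50% was never reached. Report the proportion ongoing and a 95% interval from resampling patients.

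**If calls have been made.** Label the answer as patient-recalled duration of effect and analyse it by Kaplan-Meier, with continuing effect censored at the call. For the 50% definition, add an interval-censored estimate from the dated week-6 and call GPE records. State that this is time to first recorded GPE below 50%, which gives no credit for a later period above it.

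**In both cases.** Apply the rules to eligible patients only (Section 3.2.2 lists "Refusal to participate" as an exclusion) and report how many consenting patients were not reached. State the assumption that call lag is unrelated to duration. Say how repeat treatment, surgery before the call, and a recalled end that conflicts with current GPE are handled in the analysis.

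**Cost.** The first option needs one reworded item and about three sentences for the estimator, plus the short statements above. The second needs no new data, provided GPE was recorded per knee. Patient-level resampling and interval censoring may need software other than SPSS.

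**What remains.** Recall error is not removed. In the simulation (100 patients, p = 20%, m = 12), Kaplan-Meier stayed centred on 9.5 months (95% of estimates 6.3–13.8, RMSE 1.9) with 30% random recall error, but moved to 10.9 (RMSE 2.6) if patients also over-recalled by 20%. The interval-censored estimate is imprecise: 10.0 (4.4–17.8).
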